### 12.3.2 Secondary Endpoints

Secondary endpoints include safety and tolerability of study treatment; PFS, DCR, DOR and OS in the all treated subjects population.

Safety and tolerability objectives will be measured by the incidence of adverse events, serious events, deaths, and laboratory abnormalities. Dates and duration of study treatment delays will also be described.

PFS is defined as the time from first dose to the date of the first documented tumor progression (per RECIST 1.1), or death due to any cause. Clinical deterioration in the absence of radiographic evidence is not considered progression for purposes of determining PFS. Subjects who die without a reported prior progression will be considered to have progressed on the date of their death. Subjects who did not progress or die will be censored on the date of their last evaluable tumor assessment.

Subjects who did not have any on study tumor assessments and did not die will be censored on the first dosing date. Subjects who started any palliative local therapy or subsequent anti-cancer therapy without a prior reported progression will be censored at the last evaluable tumor assessment prior to initiation of the palliative local therapy or subsequent anti-cancer therapy, whichever procedure occurred first. PFS rate at 6 months is defined as the rate from Kaplan-Meier estimate 6 months after first dosing date.

Disease control rate is defined as the number of subjects with a BOR (per RECIST v1.1 criteria) of confirmed CR or PR or SD (stable disease), divided by the number of treated subjects.

Duration of response will be summarized among subjects with objective response in and is measured from the time at which the criteria for objective response are first met until the date of a progression event (according to the definition of PFS). Subjects with objective response who does not have a progression event will be censored at the same time they were censored under the definition of PFS.

Overall survival is defined as the time from first dosing date to the date of death. A subject who has not died will be censored at last known alive date. The overall

survival rate at 6 months is the rate from Kaplan-Meier estimate 6 months after dosing date.

### 12.3.3 Exploratory Endpoint(s)

All biomarker measures, T-cell response, immune phenotype and inflammatory response evaluation will be listed, tabulated, and where appropriate plotted. Tumor tissue IHC, functional analysis and genomic analysis will be listed, tabulated and where appropriate plotted. For the continuous data, summary statistics and the corresponding changes (or percent changes) from baseline will be provided at each time-point of assessment as well as for the changes from baseline to the peak value. Categorical data will be summarized as appropriate. Subjects will be grouped by dose level or clinical response. As this is an open-label study without a control treatment, statistical analyses will be done to aid in the understanding of the results. The associations of biomarkers with dose, clinical response, or time-to-event endpoints may be assessed using the appropriate statistical methods (analysis of variance [ANOVA], categorical, or survival model), depending on the endpoint. Correlation of baseline expression levels or changes in expression levels with response or time-to-event endpoints will identify potential responsive (or resistant) subgroups.

The ctDNA and IMG objectives will be measured from serum concentration. Response characteristics will be summarized descriptively and are further described in the statistical analysis plan.

Other exploratory endpoints are discussed in details in the statistical analysis plan.

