#### 2.4.2.2 Serum and Plasma Studies:

Various factors that may impact the immunomodulatory properties and efficacy of nivolumab and ipilimumab will be investigated in peripheral blood specimens

taken from all subjects prior to or during treatment. Data from these investigations will be evaluated for associations with response, survival, and/or safety (adverse event) data. Plasma samples will be obtained at baseline, on treatment and at progression.

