#### **4.6 Duration of Therapy**

Treatment will be continued for up to 2 years or discontinuation due to toxicity, withdrawal of consent, or study closure. Subjects may discontinue either drug and remain on the other agent if certain circumstances are met ([Section 5.2.7](#)).

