## 9. STUDY CALENDAR

	Screening (0-28 day pre-dose)	Cycle 1			Cycle 2, 3, etc.			End of Treatment (EOT) Assessment n	Follow-Up Visit 30 days post EOT/ 90 days post EOT	Survival/ FU visits l
		D1	D15	D29	D1	D15	D29			
CLINICAL ASSESSMENTS										
Informed consent	X									
Inclusion/Exclusion Criteria	X									
Demographics	X									
Medical history	X									
Physical exam o	X	X	X	X	X	X	X	X	X	
Vital signs, Height (baseline), Weight, O 2 Sat	X	X	X	X	X	X	X	X		
Height (baseline), Weight, O 2 Sat	X	X	X	X	X	X	X	X		
ECOG performance status	X	X	X	X	X	X	X	X	X	
CBC w/diff, plts	X	X f	X f	X f	X f	X f	X f	X	X	
Serum chemistry a	X	X f	X f	X f	X f	X f	X f	X	X	
Hepatitis Panel b	X									
TSH, Free T4, Free T3 c	X				X			X		
EKG	X	X f								
Urinalysis	X									
Pregnancy Test (WOCBP only) d	X	X			X					
Tumor Assessment/Imaging e	X				X				X m	
TREATMENT										
Nivolumab		X g	X g	X g	X g	X g	X g			
Ipilimumab		X g			X g					
CORRELATIVE STUDIES										
Archival Tumor h	X									
Fresh Tumor Biopsy i (Second stage only)	X				X					
Plasma for Immunogenecity Studies (Second stage only) j		X	X	X	X				X	
Plasma for ctDNA (Second stage only) j		X	X	X	X				X	
OTHER ASSESSMENTS										
Concurrent meds	X	X	X	X	X	X	X	X	X	
Symptom/Toxicity Assessment j	X	X	X	X	X	X	X	X	X	

Survival Status/Subsequent Therapy									X

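### Section 12.3.3 sets no time window for the plasma-marker peak, so the peak rises by chance with time on treatment and tilts response and PFS comparisons (minor; exploratory analysis only)

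*Combined protocol and SAP*

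**What the plan says.** For continuous biomarker data, section 12.3.3 states that "summary statistics and the corresponding changes (or percent changes) from baseline will be provided at each time-point of assessment", and continues "as well as for the changes from baseline to the peak value". The next steps are grouping ("Subjects will be grouped by dose level or clinical response") and association: biomarkers against response or time-to-event endpoints "may be assessed using the appropriate statistical methods (analysis of variance [ANOVA], categorical, or survival model"). It adds that correlation of baseline levels or "changes in expression levels with response or time-to-event endpoints will identify potential responsive (or resistant) subgroups". No peak window, landmark, adjustment for number of samples or multiplicity rule is given. The section defers other detail to a statistical analysis plan, but the text available defines no peak.

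The study calendar (section 9) marks plasma for ctDNA and for immunogenicity at C1D1, C1D15, C1D29, day 1 of the repeating column for cycle 2 onward, and the post-treatment follow-up visit. No footnote ends the series. Section 2.4.2.2 is equally open-ended: "Plasma samples will be obtained at baseline, on treatment and at progression". A cycle is 42 days (4.1.2). On duration, section 4.6 says: "Treatment will be continued for up to 2 years". Progression is a reason for removal (4.9), with treatment beyond progression permitted under conditions (5.3).

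**The concern.** Treatment normally stops at progression, so the number of plasma draws is itself a consequence of outcome. Responders must also stay under assessment long enough for confirmation at least 4 weeks later (12.3.1). The maximum of several noisy values grows with their number even when the marker never changes. An open-ended peak compared between response groups, or related to PFS, therefore favours subjects who do well for a reason unrelated to biology.

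What is at stake is exploratory objective 1.3.1. A plasma marker could be reported as tracking response or PFS when it reflects only length of sampling. No primary or secondary conclusion, and no stage 1 decision, depends on this.

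**Working it through.** The plan states no figure for this analysis, so there is none to reproduce. The check builds on the calendar.

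**Draws per subject.** Post-baseline plasma falls at weeks 2 and 4, then every 6 weeks from week 6.
- By week 6: 2 + 1 = 3.
- By week 52: 2 + 8 (weeks 6 to 48) = 10.
- By week 104: 2 + 17 (weeks 6 to 102) = 19. Counting only the day-1 draws inside 17 full cycles gives 18.

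**Expected peak of pure noise.** Let D = max(Z1, ..., Zk) - Z0 with independent standard normal errors. Any stable subject level cancels in the change, so the unit is the within-subject SD and E[D] = E[max of k].

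| k | 3 | 6 | 10 | 18 | 19 |
|---|---|---|---|---|---|
| E[max], SD | 0.85 | 1.27 | 1.54 | 1.82 | 1.84 |

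A two-year subject therefore peaks about 1.84 - 0.85 = 1.0 SD above a week-6 progressor by chance. That compares two extreme individuals, not two response groups.

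**Response groups.** Inputs from the documents: scans every 6 weeks (11.1), and median PFS of 3.9 months (placebo) and 11 months (everolimus) from the trials cited in section 2.1. Stage 2 has 56 - 20 = 36 subjects (12.2), and the calendar row reads "Plasma for ctDNA (Second stage only"). Assumptions: exponential PFS for non-responders with sampling to the progression scan; responders with 10 or 18 draws; 5 or 8 responders of 36; Welch test at two-sided 5%; no true effect; follow-up draws left out.

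| Non-responder median PFS | Responders with 10 draws | Responders with 18 draws |
|---|---|---|
| 3.9 months | 8-9% | 15-21% |
| 11 months | 5-6% | 8-11% |

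The mean responder excess runs from about 0.03 SD (11 months, 10 draws) to about 0.6 SD (3.9 months, 18 draws). Further runs at the same medians reached about 23%, so the range is about 5-23%. Adding two follow-up draws for everyone lowers the 3.9-month rates to about 7% and 12-15%.

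A second set of runs used one-way ANOVA, assumed median time on treatment of 12-48 weeks (non-responders) against 36-78 weeks (responders), and within-subject correlation of 0.3 or 0.7. It gave 4.8-8.7% with 5 of 36 responding, 4.9-11.4% with 8 of 56, and 5.8-15.3% with 14 of 56. The responder mean was higher in every scenario.

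**Peak against PFS.** Same medians, 36 or 56 subjects, follow-up of 26-104 weeks, Cox score test at 5%, null marker. The test rejects in about 14-24% of trials, nearly always in the direction of higher peak with longer PFS. If follow-up draws are counted for progressors, the rate is about 6-11%.

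**With a common window.** Limiting the peak to C1D15, C1D29 and C2D1 gives 4.5-5.4% for response groups, with a mean difference of -0.01 to 0.01 SD. For PFS it gives 2-5%, so no inflation remains.

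**The case against.** Several objections have force.

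- **Status.** The analysis is exploratory and the tests are only permitted, not required. The peak appears among descriptive summaries. The association sentence does not name it, and the subgroup sentence speaks of changes in expression levels. That a peak change would be tested is a permitted reading, not a stated plan. This stands, and it is why the point is minor.
- **Unbiased summaries are already planned.** Changes at each time point, including C1D15, C1D29 and C2D1, are in the same sentence. That also stands, but it does not repair the peak summary beside them.
- **Scope.** Tissue has one scheduled on-treatment biopsy, at week 6-8, so its peak does not grow with time on treatment. The point covers serial plasma markers only. PBMC time points are referred to the calendar (8.2.2), which has no row for them.
- **Extra draws for progressors.** The follow-up visit and the progression sample give early progressors more than three values. This reduces the bias but does not remove it.

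Three stronger readings are tempting, and the documents do not support them.

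- A reader might infer false-positive rates of 20-48%. That needs every non-responder to stop at exactly 3 draws and every responder to have 10 or 18. At the cited medians, only 1 - 2^(-6/17.0) = 22% (3.9 months, about 17.0 weeks) or 1 - 2^(-6/47.8) = 8% (11 months, about 47.8 weeks) would progress by week 6, and non-responders include stable disease.
- A reader might infer guarantee-time bias when week 6-8 biopsy change is related to PFS or OS from first dose. All subjects with paired biopsies share the same event-free lead-in, so high- and low-change subjects are treated alike. In a null simulation, the Cox estimate from first dose equalled the week-7 landmark estimate in every run, with type I error of 4.4%. What remains is that results do not extend to subjects who progress earlier: 22-28% by weeks 6-8 at 3.9 months, 8-11% at 11 months.
- A reader might take grouping by dose level as a flaw. Section 1.4 assigns one regimen to everyone, so the grouping is empty, but it biases nothing.

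**Conclusion.** The concern holds for serial plasma markers. As written, section 12.3.3 permits a peak over a number of draws that depends on outcome, and the chance excess runs toward responders and longer PFS. Its size is modest for response groups: near nominal when non-responders also stay on treatment long, and highest when they progress early and all responders are sampled for about two years. It is larger for PFS, because PFS itself sets the number of draws, and roughly halves when follow-up draws count.

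The figures rest on exponential PFS, medians borrowed from other treatments, independent errors in the main runs, assumed responder counts, and the calendar mark being read as every later cycle. Whether 36 or 56 subjects give plasma is itself unclear: the calendar limits it to the second stage, while section 8 says all patients. Severity is minor.

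**What to change.** In section 12.3.3:

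- Define peak change for plasma markers over draws common to all subjects: C1D15, C1D29 and C2D1 against C1D1. State how subjects missing one of these draws are handled.
- Describe later draws by visit only.
- Analyse any later on-treatment change against PFS or OS from a stated landmark among subjects event-free then, or as a time-dependent covariate.
- For the paired biopsies, note that findings do not extend to subjects who progress before weeks 6-8.

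The cost is wording only, with no new samples or visits. The downside is small: late peaks are described rather than tested, and subjects with events before the landmark leave that analysis.

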## 12.4 Efficacy Analyses

### 12.4.1 Methods for Primary Endpoints

Among all treated subjects, the ORR will be summarized by binomial response rates and their corresponding two-sided 95% exact CIs using Clopper-Pearson method. The null hypothesis will be rejected if the 2-sided 95% CI lower bound for the ORR radiology assessed estimate is greater than 15%.

To further characterize the response: time to objective response, depth of response and BOR by response category will be summarized using descriptive statistics.

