### 12.2 Sample Size/Accrual Rate

The optimal two-stage design to test the null hypothesis that  $P \leq 0.050$  versus the alternative that  $P \geq 0.150$  has an expected sample size of 29.51 and a probability of early termination of 0.736. If the regimen is actually not effective, there is a 0.097 probability of concluding that it is (the target for this value was 0.100). If the regimen is actually effective, there is a 0.199 probability of concluding that it is not (the target for this value was 0.200). After testing the drug on 20 patients in the first stage, the trial will be terminated if 1 or fewer respond. If the trial goes on to the second stage, a total of 56 patients will be studied. If the total number responding is less than or equal to 4, the regimen is rejected.

Assuming a 15% screening failure rate, it is estimated that approximately 64 subjects will be enrolled in order to achieve 56 treated subjects.

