### 12.3 Analysis and Summary of Endpoints

#### 12.3.1 Primary Endpoints

The primary endpoint is ORR (per RECIST v1.1 criteria) among all treated subjects. All treated subjects is defined as all subjects who received at least one complete dose of nivolumab and ipilimumab. ORR is defined as the number of subjects with a best overall response (BOR) of confirmed CR or PR, divided by the number of treated subjects.

BOR is defined as the best response designation, recorded between baseline and the date of objectively documented progression per RECIST 1.1 or the date of initiation of palliative local therapy or the date of initiation of subsequent anticancer therapy,

whichever occurs first. For subjects without documented progression or palliative local therapy or subsequent anti-cancer therapy, all available response designations will contribute to the BOR determination. For subjects who continue treatment beyond progression, the BOR will be determined based on response designations recorded up to the time of the initial RECIST 1.1-defined progression.

Complete or partial responses may be claimed only if the criteria for each are met at a subsequent time point of  $\geq 4$  weeks later.

Further characterization of the response will include time to objective response (time from first dosing date to first CR or PR) and depth of response (maximum tumor shrinkage in target lesions).

The analysis of the primary endpoint ORR will be performed six months after the last subject's first treatment.

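### The primary analysis in section 12.4.1 (95% Clopper-Pearson interval, lower bound above 15%) does not apply the decision rule, null rate or error level of the Simon design in section 12.2

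*Combined protocol and SAP*

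**What the plan says.** Section 12.2 tests a null response rate of at most 5% against an alternative of at least 15%. The first stage reads: "After testing the drug on 20 patients in the first stage, the trial will be terminated if 1 or fewer respond". If the trial continues, "a total of 56 patients will be studied". The final rule is: "If the total number responding is less than or equal to 4, the regimen is rejected". Success is therefore 5 or more responses in 56. The stated error rates are 0.097 (type I, target 0.100) and 0.199 (type II, target 0.200), and the design "has an expected sample size of 29.51 and a probability of early termination of 0.736".

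Section 12.3.1 defines ORR as confirmed responders "divided by the number of treated subjects". Section 12.4.1 says "the ORR will be summarized by binomial response rates and their corresponding two-sided 95% exact CIs using Clopper-Pearson method", and then makes the interval a decision rule: the null is rejected if the lower 95% limit is above 15%. Neither 12.3.1 nor 12.4.1 refers to the stage 1 stop, to the 4/56 boundary or to the design alpha. Section 12.3.3 points to a statistical analysis plan, but for response characteristics and exploratory endpoints, not for the primary test.

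**The concern.** The plan holds two rules for one hypothesis. They differ in the threshold (5% in 12.2, 15% in 12.4.1), in the one-sided error level (9.7% against 2.5%), and in whether the two-stage sampling is taken into account. A result between the two boundaries would be a success under one section and a failure under the other, with nothing in the document to say which prevails. If only the threshold were corrected to 5%, the report could still show a positive decision beside a 95% interval that contains the null rate.

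**Working it through.** **Inputs.** From 12.2: null 0.05, alternative 0.15, stop at 1 or fewer of 20, 36 more patients, success at 5 or more of 56. From 12.4.1: two-sided 95% Clopper-Pearson (CP), lower limit above 15%.

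**1. The design reproduces.** With X1 ~ Bin(20, p) and X2 ~ Bin(36, p), P(success) = sum over x1 = 2 to 20 of P(X1 = x1) × P(X2 ≥ 5 − x1).
- p = 0.05: 0.0967 (stated 0.097).
- p = 0.15: 0.8010, so type II error 0.1990 (stated 0.199).
- Early termination at p = 0.05: 0.95^20 + 20 × 0.05 × 0.95^19 = 0.3585 + 0.3774 = 0.736 (stated 0.736).
- Expected sample size: 20 + 36 × (1 − 0.7358) = 29.51 (stated 29.51).

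**2. The 15% rule.** The CP lower 95% limit is the 0.025 quantile of Beta(s, 56 − s + 1). It is 14.4% at 14/56 and 15.8% at 15/56, so the rule needs 15 responses. Its probability of success, with the stage 1 stop in force, compared with the 12.2 rule:

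| True ORR | 5 or more of 56 | 15 or more of 56 |
|---|---|---|
| 15% | 80.1% | 1.6% |
| 20% | 92.8% | 13.6% |
| 25% | 97.5% | 42.8% |
| 30% | 99.2% | 74.4% |

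Outcomes of 5 to 14 responses succeed in 12.2 and fail in 12.4.1. At a true ORR of 15% their probability is 0.801 − 0.016 = 0.785. Allowing for the stop does not move this boundary: the two-stage lower limits are also 14.4% and 15.8%.

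**3. The 95% interval against the 5% null.** Two-stage limits come from solving P(reach stage 2 and S ≥ s | p) = tail level (stage-wise ordering).

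| Responses | CP lower 95% | CP upper 95% | Two-stage lower 95% |
|---|---|---|---|
| 5/56 | 2.96% | 19.6% | 3.36% |
| 6/56 | 4.03% | 21.9% | 4.33% |
| 7/56 | 5.18% | 24.1% | 5.39% |

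Both methods include 5% at 5/56 and 6/56 and exclude it at 7/56. The level is the cause here, not the stop. The probability of a design success at 5 or 6 responses is 0.079 at true 5% (0.079/0.097 = 82% of successes) and 0.121 at true 15% (0.121/0.801 = 15%).

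**4. The design's own level.** At 5/56 the one-sided p-value for 5% is 0.097 two-stage and 0.147 as a plain binomial. The one-sided 90% lower bound is 4.41% by CP and 5.05% two-stage, so only the two-stage bound agrees with the decision. At 6/56 both exceed 5% (5.73% and 6.19%). The probability of exactly 5/56 with the trial in stage 2 is 5.2%, 10.5% and 4.3% at true ORR 5%, 10% and 15%.

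**5. Coverage of the 95% CP interval under the two-stage design.** It is 98.3%, 97.9% and 97.9% at true 5%, 10% and 15%, 95.5% at 20% and 95.0% at 25%. On a grid of 0.25 points from 2% to 30% the lowest value is 93.9%, at 26.25%: misses are 2.25% (lower limit too high), 1.84% (early stops with upper limit too low) and 2.01% (stage 2, upper limit too low), total 6.10%.

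**6. Bias of the raw ORR.** Over all trials, E[responses/treated] − p is −1.15, −1.65 and −1.25 points at true 5%, 10% and 15%. Among trials that reach stage 2 the mean raw ORR is 7.4%, 11.5% and 15.8%, above the truth each time.

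**The case against.** The case for the present text is that Clopper-Pearson is a standard, cautious summary and that 12.2 already states the decision rule, so the interval need only describe. Its first half stands: coverage is nominal or better from 5% to 20%, and the one shortfall found is small and lies well above the alternative. Its second half fails, because 12.4.1 attaches a rejection rule to the interval. One might also take the 15% bar as a deliberate stricter target. The documents do not say so: 12.4.1 presents it as the test of the null, and the only null stated is 5%.

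A reader might infer more than the documents support:
- That ignoring the stopping rule is what makes the interval contradict the decision. At the planned 95% level it is not, since the two-stage interval includes 5% at the same two outcomes.
- That at 5/56 the interval says the opposite of success. It runs from 3.0% to 19.6% and contains both the null and the alternative, so it is inconclusive.
- That the raw ORR is simply biased down. That is true only on average over trials including early stops; it is biased up in those that continue.
- That the uniformly minimum variance unbiased estimate (UMVUE) should replace the raw rate. At 5/56 it is 12.5% against 8.9%. It is unbiased overall, but at true 5% its root mean square error is 4.7 points against 3.5, and among stage 2 trials it averages 11.8%. The choice is a trade-off, not the repair of an error.

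**Conclusion.** The point holds as a mismatch between design and analysis. Its largest part is the 15% threshold, which moves the boundary from 5/56 to 15/56 and cuts power at the alternative from 80.1% to 1.6%. Next is the confidence level, which leaves 5% inside the interval at two successful outcomes. The smallest part is the unadjusted stage 1 stop, which changes the reading at 5/56 alone and biases the raw ORR by at most about 1.7 points over the whole design. The results do not show an invalid interval.

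The figures assume exactly 20 and 56 treated subjects, independent responses with a common rate, and the stage 1 rule applied as written. Other treated counts would shift the limits.

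**What to change.** In 12.4.1:
- State that the decision follows 12.2: the null is rejected at 5 or more responses in 56 after passing stage 1. Remove the rule that the lower limit must exceed 15%. If a 15% bar is wanted for another purpose, name it as separate and give its power.
- Report a two-stage exact one-sided 90% lower bound, or the 80% two-sided interval, using stage-wise ordering. At 5/56 the 80% interval is 5.05% to 19.0%, against 4.4% to 15.9% by Clopper-Pearson.
- Keep the raw proportion and the 95% Clopper-Pearson interval, labelled descriptive. The UMVUE may be added as a supplement, with a note on the sense in which it is unbiased.

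The cost is a change of wording, a few lines of code and a second interval to explain. Sample size and conduct are unaffected. If two-sided two-stage intervals are shown at low counts, their upper limits are markedly higher: at 2/56 the 95% upper limit is 24.9%, against 12.3% by Clopper-Pearson. A one-sided lower bound avoids that.

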## 12. STATISTICAL CONSIDERATIONS

### 12.1 Study Design/Endpoints

This is an open label, phase II clinical trial of nivolumab and ipilimumab in subjects with advanced, well-differentiated nonfunctional NET of the pancreas, lung or gastrointestinal (GI) tract. The primary endpoint is ORR defined as RECIST 1.1 partial response (PR) or complete response (CR).

Simon two-stage design (28) was used to evaluate the primary endpoint, with details as described in section 12.2.

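### Sections 12.2 and 12.4.1 give conflicting success rules for the primary endpoint; applying the 12.4.1 rule cuts power at the 15% design rate from 80% to about 2%

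*Combined protocol and SAP*

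**What the plan says.** Section 12.1 names the design and points to 12.2 for its details: "Simon two-stage design (28) was used to evaluate the primary endpoint, with details as described in section 12.2".

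Section 12.2 sets the null at a response rate of 5% or less and the alternative at 15% or more. The stage 1 rule is: "After testing the drug on 20 patients in the first stage, the trial will be terminated if 1 or fewer respond". The final rule, on 56 patients, is: "If the total number responding is less than or equal to 4, the regimen is rejected". Success therefore means 5 or more responders. The section gives a type I error of 0.097 and a type II error of 0.199, so power is 0.801.

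Section 12.4.1, on methods for the primary endpoint, says that the response rate will be summarized with a two-sided 95% Clopper-Pearson interval among all treated subjects. It then adds a rejection rule: "The null hypothesis will be rejected if the 2-sided 95% CI lower bound for the ORR radiology assessed estimate is greater than 15" per cent.

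No section states a 15% null, and none says which rule takes precedence.

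**The concern.** A confidence-interval rule that rejects a null of 5% compares the lower limit with 5%. Section 12.4.1 compares it with 15%, the rate that 12.2 treats as the target. To clear that bar the observed rate must lie well above the rate that the trial was sized to detect.

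A regimen performing exactly at the design target would therefore nearly always fail 12.4.1 while usually passing 12.2. Section 12.4.1 is also where an analyst would look for the test. The trial is open-label and section 11.1.7 plans no central radiology review, so leaving two rules in place would allow the criterion to be chosen once the responses are known.

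**Working it through.** **Inputs.** From 12.2: null rate 0.05, alternative rate 0.15, stage 1 of 20 patients (stop at 1 or fewer responders), total 56, success at 5 or more. From 12.4.1: two-sided 95% Clopper-Pearson interval, lower limit above 15%. From 12.3.1: the denominator is all treated subjects, taken here as the planned 56.

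**Formula.** For a final cutoff of c responders and a true rate p,

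P(success) = Σ (x = 2 to 20) Bin(x; 20, p) × P(Y ≥ c − x), with Y ~ Bin(36, p).

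**Step 1. Reproduce the plan's figures (c = 5).**
- Probability of early termination at p = 0.05: P(0 of 20) + P(1 of 20) = 0.3585 + 0.3774 = 0.7358 (plan: 0.736).
- Expected sample size at p = 0.05: 20 + (1 − 0.7358) × 36 = 29.51 (plan: 29.51).
- Type I error: 0.0967 (plan: 0.097).
- Power at p = 0.15: 0.8010, so the type II error is 0.199 (plan: 0.199).

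All the 12.2 figures reproduce. The sample size is sound and the fault lies in 12.4.1.

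**Step 2. Find the cutoff that 12.4.1 implies.** The Clopper-Pearson lower limit for x of n is the 0.025 quantile of Beta(x, n − x + 1). With n = 56:

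| Responders | Observed rate | 95% lower limit |
|---|---|---|
| 5 | 8.9% | 2.96% |
| 6 | 10.7% | 4.03% |
| 7 | 12.5% | 5.18% |
| 14 | 25.0% | 14.39% |
| 15 | 26.8% | 15.83% |

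The smallest count with a lower limit above 15% is 15, three times the Simon cutoff of 5.

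**Step 3. Compare the two rules, both with the stage 1 stop.**

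| True response rate | P(success), 12.2 (≥5 of 56) | P(success), 12.4.1 (≥15 of 56) | P(rules disagree) |
|---|---|---|---|
| 5% | 9.7% | 0.000007% | 9.7% |
| 15% | 80.1% | 1.6% | 78.5% |
| 20% | 92.8% | 13.6% | 79.2% |
| 25% | 97.5% | 42.8% | 54.8% |
| 30% | 99.2% | 74.4% | 24.8% |

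The last column is the probability of passing stage 1 and ending with 5 to 14 responders, which is the difference between the two columns before it (at 15%: 0.8010 − 0.0158 = 0.785). Under 12.4.1, 80% power is reached at a true rate of about 31.2%.

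**Step 4. Test whether 15% is simply a slip for 5%.** With a 5% threshold and the same 95% interval, 7 responders are needed (6 give 4.03%, 7 give 5.18%). The two-stage type I error is then 0.017 and power at 15% is 0.680. Counts of 5 or 6 would still split the two sections. The reason is that a two-sided 95% interval works at one-sided 2.5%, whereas the design works at one-sided 10%.

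**Step 5. Test whether another confidence level rescues the 15% threshold.** A 90% interval needs 14 responders (power 3.4% at 15%) and an 80% interval needs 13 (power 6.8%). Neither comes near the stated power.

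**The case against.** The strongest reply is that 12.1 assigns the evaluation of the primary endpoint to the Simon design and refers to 12.2, so 12.2 governs and the 12.4.1 sentence is a stray. On that reading power stays at 0.801. This is fair as far as it goes: the 1.6% applies only if 12.4.1 is followed. But 12.1 does not say that 12.2 overrides 12.4.1, and the sentence in 12.4.1 is worded as a rejection rule, not as description.

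A second reply is that the error is conservative. That is true: under 12.4.1 a false claim of activity at a 5% rate is almost impossible, and the stage 1 stop is unaffected. The harm runs the other way, as a missed active regimen or an ambiguous verdict.

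Two smaller points also stand. The documents do not say how 15% came to be in the sentence; what can be shown is that it equals the design alternative and contradicts 12.2. And the cutoff of 15 depends on the number treated: it holds for 54 to 58 subjects, falls to 14 for 50 to 53 and rises to 16 for 59 to 62. None of this removes the conflict.

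**Conclusion.** The concern holds and must be fixed. The plan has two incompatible decision rules for its primary endpoint. If 12.4.1 is applied, power at the 15% design rate is 1.6% instead of 80.1%. If neither rule is withdrawn, the trial has a 78.5% chance at that rate of a result that the two sections classify in opposite ways. Only the 12.2 rule gives the error rates that the plan states.

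These figures are exact binomial calculations. They assume 56 treated subjects if stage 2 opens, independent responses with a common rate, and the stage 1 stop applied as written.

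**What to change.** Remove the 15% lower-limit criterion from 12.4.1. State there that the null (response rate of 5% or less) is rejected if at least 2 of the first 20 subjects respond and at least 5 of 56 treated subjects have a confirmed response, as 12.2 implies. Keep the two-sided 95% Clopper-Pearson interval and label it descriptive.

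If an interval that agrees with the test is wanted, use one adjusted for the two stages (for example Koyama-Chen) and compare its one-sided 90% lower limit with 5%. An unadjusted one-sided 90% Clopper-Pearson limit at 5 of 56 is 4.4%, so it would still disagree with the Simon rule. This addition is optional.

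Make the change in a dated amendment before the primary analysis. If responses are already known, report the result under both rules and say when the change was made. The cost is a short wording change plus the amendment process, with no extra patients, data or change to treatment.
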